**Table 1**

PERIOD	TIMING	PROCEDURES
ADP	10 am	Breath alcohol levels, AUQ, YCS, TLFB, SAFTEE, CADSS, Vitals Administer last doses of medications
	11 am	Approach Avoidance Task, Impulsivity tasks; Self report and Laboratory measures
	12 pm	Lunch and Smoke Break for smokers
	1 pm	Insertion of IV for blood alcohol draws
	2 pm	Start of baseline; AUQ, YCS, BAES, Vitals; Smoke break for smokers
	2:30 pm	AUQ, YCS, BAES, Vitals
	2:45pm	YCS
	2:50 pm	Alcohol cue exposure to preparation of priming drink (PD)
	2:59 pm	YCS
	3 pm	Priming dose period: Instruct participant to consume PD (0.03g/dl) in five minutes

	3:10 pm	Blood alcohol, AUQ, YCS, BAES
	3:20 pm	Blood alcohol, AUQ, YCS, Vitals
	3:30 pm	Blood alcohol, AUQ, YCS, BAES
	3:40 pm	Blood alcohol, AUQ, Vitals
	3:50 pm	Blood alcohol, AUQ, YCS, BAES
	4 pm First tray	1 st Self-administration (SA) period: Bring in first tray of 4 drinks (each designed to raise BAL by .015 g/dl) and drinking tab (\$12); Instruct participants on choice of drinks versus money.
	4:30 pm	AUQ, YCS, BAES
	5 pm Second tray	Blood alcohol, AUQ, BAES, Vitals @ 4:55 pm 2 nd SA period: Remove first tray and bring in second tray: Present participant with 4 drinks (each will raise BAL by .015 g/dl) and drinking tab (\$12); repeat instructions
	5:30 pm	AUQ, YCS, BAES
	6 pm Third tray	Blood alcohol, AUQ, BAES, Vitals @ 5:55 pm 2 nd SA period: Remove second tray and bring in third tray: Present participant with 4 drinks (each will raise BAL by .015 g/dl) and drinking tab (\$12); repeat instructions
	6:30 pm	AUQ, YCS, BAES
	7 pm	Blood alcohol, AUQ, BAES, YCS, Vitals
	7:30 pm	Dinner
	8 pm	Breath Alcohol, AUQ, YCS, BAES, Vitals
	9 pm	Breath Alcohol, AUQ, YCS, BAES, Vitals
	10 pm	Breath alcohol, AUQ, YCS, BAES, Vitals
Discharge	7 am	Breath alcohol, AUQ, YCS, Vitals, CADSS, BPRS

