*Yale Craving Scale (YCS)*: We have been collaborating with [name] to develop this craving measure based on psychophysiological scaling methods. In her work on individual differences in the ability to taste bitterness, [name] and colleagues (Marks et al., 1988) used magnitude-matching procedures (Stevens and Marks, 1980) in which participants matched the intensity of perceived bitterness to sounds. By doing so, the problem of differences in how labels (e.g., very strong) are applied was circumvented by making the comparison to a standard that is unrelated to taste. The resulting scale, Labeled Magnitude Scale (gLMS) (Bartoshuk, 2002), has been extended to measure hedonic ratings for foods, and we have adapted it for rating craving for tobacco and alcohol. It is not subject to the ceiling effects that often occur in craving research (Sayette et al., 2000). We have been collecting craving data using this scale in our ongoing projects and the findings from this scale have been found to parallel those obtained using the Alcohol Urge questionnaire. *A significant advantage of this scale is that following completion of baseline training to match perceived intensity of craving to the perceived brightness from the sun, each assessment timepoint only consists of a single visual analog scale of craving, making it very easy to administer.*

f) Clinical Institute Withdrawal Assessment for Alcohol-Revised (CIWA-Ar): This is a modified, shorter version of the Clinical Institute Withdrawal Scale for Alcohol which is equally efficient and reliable as the original scale without a significant loss in accuracy. The CIWA-Ar is a 10 item scale that contains alcohol withdrawal signs and symptoms that include nausea/vomiting, tremor, headache, anxiety, agitation, orientation, sweating, and auditory, visual, and tactile disturbances. This tool often guides the clinical management of alcohol (Sullivan et al., 1991) withdrawal (for a review, see Saitz and O'Malley, 1997) and is used extensively in research on alcohol withdrawal (Sellers et al., 1991; Saitz et al., 1994).

g) Psychiatric and mood symptoms: We will assess changes in these symptoms during Days 1-13 using:

*Positive and Negative Syndrome Scale (PANSS)* (Chapman et al., 1980): A clinician-rated general assessment measure used to measure psychosis (positive symptoms), emotional or motivational deficits (negative symptoms), and thought disorder.

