*Clinician-Administered Dissociative States Scale (CADSS)* (Bremner et al., 1998): A 19 item self-report questionnaire with eight observer ratings designed to assess perceptual, behavioral, and attentional changes that occur during dissociative experiences from NMDA receptor antagonists (Krystal et al., 1994).

h) Intellectual Functioning: In order to obtain an assessment of general intellectual functioning and a reference point for other cognitive assessments, we will complete the two subtest short-form of Block Design and Information from the WAIS-III (Weschler, 1997). This combination correlates at .87 with the Full Scale IQ.

i) Impulsivity and Automatic Motivational Measures: Change from occasional to compulsive drug use may be less dependent on positive reinforcement and more dependent on implicit processes that automatically evaluate the motivational significance of the alcohol cue for affect regulation. Such processes may include “fast” impulsive responses which automatically orient the individual to either approach or avoid the stimulus and “slower,” more reflective processes involving conscious deliberation and emotion regulation. We will assess using impulsive responding using measures which encompass several clinically relevant core components such as rapidity of response, degree of planning, and disregard of future consequences. Additionally, we will also measure implicit alcohol-affect associations as well as individual variations in the ability of incentive stimuli to control behavior. We will evaluate changes in impulsivity and implicit alcohol associations at baseline and then after each medication period. Pavlovian to Instrumental transfer task will be assessed at baseline only.

j) Padua Inventory (Sanavio, 1988): consists of 60 items describing common obsessional and compulsive behavior and allows investigation of the topography of such problems in normal and clinical symptoms.

k) Chronic Stress Scale (CSS) (Turner et al., 1995): This measure is used to assess a person's perception of ongoing and enduring sources of stress in their life conditions. The chronic stress scale (CSS) includes a list of 51 items about common life conditions and situations (e.g., financial issues, work, marriage and relationship, parental, family, social life). The interviewer reads each item aloud and asks the respondent to reply with not true (0), somewhat true (1), or very true (2).

*Self Reports:*

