i) Psychophysiological Measures: These will include heart rate and blood pressure monitored using a Critikon Dinamap while skin temperature will be measured using Yellow Springs Instruments 4600 precision thermometer. The cuff of the Dinamap will be on the subject's dominant arm while the probe of will be attached to the middle finger of the subject's non-dominant arm. These data will be further used to examine the safety of using the medication combination during alcohol self-administration.

4. **Statistical Considerations:** Describe the statistical analyses that support the study design.

All outcomes will be summarized descriptively and assessed for normality prior to analysis using normal probability plots and Kolmogorov test statistics. Transformations or nonparametric analyses will be performed as necessary. In the mixed models described below, the correlation between repeated measures on an individual will be modeled using random effects and/or structured variance-covariance matrices. The best-fitting variance-covariance structure will be determined by information criterion. The mixed-effects approach is advantageous in that it is unaffected by randomly missing data and allows greater flexibility in modeling the correlation structure of repeated-measures data (Gueorguieva and Krystal, 2004). In the models below, we will test for order effects, although any such effects should be greatly minimized with the inclusion of the baseline session. All tests will be two-sided and considered statistically significant at alpha=.05. Significance levels for secondary comparisons will be adjusted for multiple tests using the Bonferroni correction, basing the adjustment on the number of conceptually related statistical tests within each hypothesis.

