Alcohol is a reinforcing agent, which may cause changes in behavior including repetitive or excessive alcohol consumption. Because of this, the administration of alcohol to alcoholics in treatment could potentially impede the progress of their recovery. In addition, the administration of alcohol to sober alcoholics living in the community presents a possible risk of relapse. As a result, we will be recruiting **non**-abstinent **non**-treatment seeking alcoholics in keeping with the National Advisory Council on Alcohol Abuse and Alcoholism's (1989) recommended guidelines on ethyl alcohol administration. At completion of the study, we will make a serious and concerted effort to link the subject with treatment for their alcohol problems. This will be done by giving the subject objective feedback about the fact that their drinking exceeds standards for avoiding hazardous drinking, providing a brief one session motivational intervention for their drinking, and by arranging for alcohol treatment services if they are interested. In our previous and ongoing work, several participants quit drinking and many others reduced their drinking in the three months following this intervention (Sinha R, Krishnan-Sarin S, Farren C, O'Malley SS. Naturalistic follow-up of drinking behavior following participation in an alcohol administration study. *Journal of Substance Abuse Treatment* 1999; 17: 159-62).

5) Interactions of Memantine and Alcohol:

There are no known interactions of co-administering memantine and alcohol. In a study by Bisaga and Evans [40] in moderate drinkers, memantine by itself produced some increase in dissociative symptoms which were further slightly increased by alcohol. Since, in this study,

participants will be taking memantine on an outpatient basis, we will monitor via face-to-face daily contact for side effects from memantine.

6) Interactions of NAC and Alcohol:

There are no known interactions of co-administering NAC and alcohol. Since, in this study, participants will be taking NAC on an outpatient basis, we will monitor via face-to-face daily contact for side effects from NAC.

7) Interactions of Naltrexone and Alcohol:

There are no known risks to contraindicate the administration of alcohol to subjects on naltrexone. It has been shown that pharmacokinetics properties of naltrexone and ethanol are not altered on simultaneous administration of both agents.

8) Intravenous Access:

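### In the drinking sessions neither CADSS nor SAFTEE is scheduled from 5 hours before the first alcohol until the next morning; adding both at 8 pm is a cheap gain in tolerability data

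*Combined protocol and SAP*

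**What the plan says.** Section IX.1, item 5 (memantine and alcohol) states "There are no known interactions of co-administering memantine and alcohol". Its next sentence reports, from a study in moderate drinkers, that "memantine by itself produced some increase in dissociative symptoms which were further slightly increased by alcohol". The memantine background in Section V.2 calls the combined effect mild.

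Section V.3, Assessments, item g, describes the CADSS as designed for "perceptual, behavioral, and attentional changes that occur during dissociative experiences from NMDA receptor antagonists". The plan for it is "We will assess changes in these symptoms during Days 1-13 using" this scale and the PANSS, with no clock times relative to drinking.

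Table 1 sets the ADP timetable:

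- 10 am: "Breath alcohol levels, AUQ, YCS, TLFB, SAFTEE, CADSS, Vitals", with the last medication doses.
- 3 pm: priming drink. Three one-hour choice periods follow from 4 pm.
- 8 pm: "Breath Alcohol, AUQ, YCS, BAES, Vitals".
- 7 am discharge: "Breath alcohol, AUQ, YCS, Vitals, CADSS, BPRS".

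Section V.3, item g of the ADP description, ends alcohol administration at 7:05 pm. Item f keeps assessments few in the choice periods so that drinking is not disturbed.

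On purpose, the Assessments text says of heart rate, blood pressure and skin temperature: "These data will be further used to examine the safety of using the medication combination during alcohol self-administration". The Power Analysis paragraph of Section V.4 names initial tolerability as something the pilot is meant to determine.

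**The concern.** The ADP is the one setting in the study where memantine and measured alcohol doses are given together under observation. The protocol names one adverse human effect of that pairing, added dissociation, and has chosen a scale for it. The timetable uses the scale before and long after the alcohol, but not while alcohol is on board. The structured adverse-event instrument, SAFTEE, does not recur in the session after 10 am.

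The measures that are taken during the session cannot stand in for it. BAES rates stimulation and sedation, the craving scales rate craving, and vitals are physiological. A transient rise in dissociation between 3 pm and late evening would reach the data only by spontaneous report, or if it lasted until 7 am. A pilot meant to inform later trials on tolerability would then have little to say on this effect.

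**Working it through.** **Timing (Table 1; ADP item g).**

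- Last CADSS and SAFTEE to first alcohol: 10 am to 3 pm = 5 h.
- End of alcohol access to next CADSS: 7:05 pm to 7 am = 11 h 55 min.
- Whole interval without CADSS: 10 am to 7 am = 21 h.
- SAFTEE: no further entry in the session, including at 7 am.

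**Assessments from 3 pm to 10 pm (Table 1).**

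| Measure | Times | Count |
|---|---|---|
| BAES | 3:10, 3:30, 3:50, 4:30, 4:55, 5:30, 5:55, 6:30, 7, 8, 9, 10 | 12 |
| Vitals | 3:20, 3:40, 4:55, 5:55, 7, 8, 9, 10 | 8 |
| CADSS | none | 0 |
| SAFTEE | none | 0 |

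**Do the outpatient ratings fill the gap?** Clinic visits are at 10 am (Section V.3, Study Medication). A CADSS taken there coincides with alcohol only by chance.

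**Is memantine still present at 8 pm?** Section VI.2 gives a peak 3 to 8 h after the dose and a half-life of 60 to 100 h. A 10 am dose peaks between 1 pm and 6 pm, so 8 pm is 2 to 7 h after the peak. Taking the longest delay and the shortest half-life, 0.5^(7/60) = 0.92. Exposure at 8 pm is at least about 92% of peak.

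**Is alcohol still present at 8 pm?** From Table 1, the priming drink targets 0.03 g/dl and each choice drink 0.015 g/dl, with at most 12 choice drinks. The documents give no elimination rate, so I assume 0.015 to 0.020 g/dl per hour, with each drink reaching its target and absorbed by 8 pm. Over the 5 h from 3 pm to 8 pm, with n drinks and hourly elimination k, the level is at least

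0.03 + 0.015n − 5k, and never below zero.

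| n | k = 0.015 | k = 0.020 |
|---|---|---|
| 3 | 0.075 − 0.075 = 0 | 0.075 − 0.100, so 0 |
| 4 | 0.090 − 0.075 = 0.015 | 0.090 − 0.100, so 0 |
| 5 | 0.105 − 0.075 = 0.030 | 0.105 − 0.100 = 0.005 |
| 12 | 0.210 − 0.075 = 0.135 | 0.210 − 0.100 = 0.110 |

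Whatever the drink timing, the 8 pm level is above zero from 4 drinks (slower elimination) or 5 drinks (faster). Lighter drinkers may be at or near zero.

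**How many memantine sessions are affected?** Each subject has two medicated sessions, but the documents do not settle how the three conditions are paired. If all pairings are equally common, two thirds of subjects have an NTX+MEM session. If everyone receives NTX+placebo and one of the two combinations, half do. For 30 completers (Power Analysis) that is 30 × 2/3 = 20 or 30/2 = 15. For the enrolment target of 86 it is 86 × 2/3 = 57 or 86/2 = 43.

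**The case against.** **Tolerability is measured elsewhere.** The Secondary Aim in Section V.1 concerns giving naltrexone with memantine or NAC, not memantine with alcohol. Daily adverse events, CADSS over Days 1-13, the 10 am ratings after the full course, the next-morning CADSS and BPRS, and follow-up at one week all serve it. This stands. A reader might infer that the tolerability aim is left unmeasured, and the documents do not support that. The gap is confined to the hours with alcohol on board.

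**The stake is low.** The reported effect was mild, subjects are supervised and stay overnight (Section IX.1, item 4), and the same ADP was used in the group's earlier memantine study. The dose justification in Section V.3 says total adverse events at 20 and 40 mg did not differ from placebo there. This also stands, although that comparison did not report dissociation under alcohol and did not involve the naltrexone combination.

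**An 8 pm rating is an imperfect probe.** The only standardised alcohol exposure is the priming dose. By 8 pm subjects have taken between 0 and 12 drinks of their own choosing. If NTX+MEM lowers drinking, as hypothesised, blood alcohol at 8 pm will be lower in that condition and could hide added dissociation. The baseline ADP always comes first, so it is not a clean alcohol-only control. All of this stands and limits what can be claimed. Rating in the absorption hour would give a standard dose, but it would put a long questionnaire immediately before the choice periods that yield the primary outcome.

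**The limit on assessments is deliberate.** Its stated reason is interference with drinking behaviour. It does not reach 8 pm, when choice drinking has ended.

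**Section IX.1, item 5, is only loosely worded.** A reader might infer that it hides an interaction or promises monitoring that will not happen. Neither holds. The sentence after the denial discloses the dissociation result, and the preclinical ataxia finding is in Section V.2. Where Section V.3 allows take-home doses, a daily phone call asks about adverse events, and the final two doses before the ADP are excluded from that exception.

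**Conclusion.** The gap in the timetable is real: no CADSS or SAFTEE falls between 5 h before the first alcohol and about 12 h after access ends, in a study that names alcohol-related dissociation on memantine and has chosen a scale for it. Its consequence is small. What is lost is modest tolerability information from 15 to 20 NTX+MEM sessions if 30 subjects complete, or 43 to 57 with 86 subjects, depending on the pairing of conditions.

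A reader might take this as an acute safety failure. The documents do not support that, given the mild reported effect, the in-session vitals and alcohol levels, and the supervised overnight stay. No primary outcome or primary analysis is affected. The point is worth acting on because the remedy is cheap.

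The timing rests on Table 1 alone. The statement that 8 pm is usually still under alcohol for subjects taking at least 4 or 5 drinks rests on the assumed elimination rates.

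**What to change.** 1. In Table 1, add CADSS and SAFTEE to the 8 pm row, for all three ADPs and all arms. Breath alcohol, BAES and vitals are already taken then, and choice drinking ended by 7:05 pm, so that session's drink count cannot be affected.
2. In Section V.4, add a sentence such as: *The change in CADSS from 10 am to 8 pm and the 8 pm SAFTEE items will be summarised by treatment condition, beside drinks consumed and 8 pm breath alcohol. These summaries are descriptive and no hypothesis will be tested.*
3. State the limits in the same place: some subjects will be near zero blood alcohol at 8 pm, comparison between conditions is confounded by differing intake, and the baseline session is always first.

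The cost per session is one CADSS (19 self-report items and 8 observer ratings) and one SAFTEE, at a time already staffed. I assume a few minutes of subject burden; the documents do not give the length of SAFTEE. Visits, sample size and the primary analysis do not change.

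Optional clarifications, separate from this fix: reword the opening of Section IX.1, item 5, to agree with its next sentence, mention there the phone-call exception to daily visits, and use a scripted SAFTEE for those calls.

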**1) Personnel responsible for the safety review and its frequency:**

We will be accessing the Data and Safety Monitoring Board (DSMB) developed for the Center for Translational Neuroscience on Alcoholism ([name], PI). The DSMB is multi-disciplinary and includes representatives with expertise in the primary components of the proposed trial. The following individuals will be on the DSMB as voting members:

[name], PhD., [name] (Brown)/ASOS Res Provid. VAMC Chmn, DSMB

[name]., Director, Decision Sci. Int., Statistician, DSMB

[name]., Dir, Dept Psychiatry Ethics Committee, IRB Rep, DSMB

[name]., [name], Fairfield Univ. Ethicist, DSMB

This DSMB will follow the operational guidelines outlined in the YCCI OR CNRU plan for DSMB.

We hope to recruit subjects at a rate of about 1-2 per month, thus, the DSMB will review safety reports two times a year. More frequent meetings will be scheduled if indicated by interim findings.

**2) The risks associated with the current study are deemed moderate for the following reasons:**

Given the now established safety and validity of the current medications in our prior work, we do not view the proposed studies as high risk.

Although we have assessed the proposed study as one of moderate risk, the potential exists for anticipated and/or unanticipated adverse events, serious or otherwise, to occur since it is not possible to predict with certainty the absolute risk in any given individual or in advance of first-hand experience with the proposed study methods. Therefore, we provide a plan for monitoring the data and safety of the proposed study as follows:

**3) Attribution of Adverse Events:**

Adverse events will be monitored for each subject participating in the study and attributed to the study procedures / design by the principal investigator, [name] according to the following categories:

- a.) Definite: Adverse event is clearly related to investigational procedures(s)/agent(s).
- b.) Probable: Adverse event is likely related to investigational procedures(s)/agent(s).
- c.) Possible: Adverse event may be related to investigational procedures(s)/agent(s).
- d.) Unlikely: Adverse event is likely not to be related to the investigational procedures(s)/agent(s).
- e.) Unrelated: Adverse event is clearly not related to investigational procedures(s)/agent(s).

**4) Plan for Grading Adverse Events:**

The following scale will be used in grading the severity of adverse events noted during the study:

1. Mild adverse event
2. Moderate adverse event
3. Severe

**5) Plan for Determining Seriousness of Adverse Events:**

**Serious Adverse Events:**

In addition to grading the adverse event, the PI will determine whether the adverse event meets the criteria for a Serious Adverse Event (SAE). An adverse event is considered serious if it:

1. is life-threatening
2. results in in-patient hospitalization or prolongation of existing hospitalization
3. results in persistent or significant disability or incapacity
4. results in a congenital anomaly or birth defect OR
5. results in death
6. based upon appropriate medical judgment, may jeopardize the subject's health and may require medical or surgical intervention to prevent one of the other outcomes listed in this definition, or
7. adversely affects the risk/benefit ratio of the study

An adverse event may be graded as severe but still not meet the criteria for a Serious Adverse Event. Similarly, an adverse event may be graded as moderate but still meet the criteria for an SAE. It is important for the PI to consider the grade of the event as well as its "seriousness" when determining whether reporting to the HIC or HSC is necessary.

**6) Plan for reporting serious AND unanticipated AND related adverse events, anticipated adverse events occurring at a greater frequency than expected, and other unanticipated problems involving risks to subjects or others to the HIC or HSC.**

The investigator will report the following types of adverse events to the HIC or HSC: a) serious AND unanticipated AND possibly, probably or definitely related events; b) anticipated adverse events occurring with a greater frequency than expected; and c) other unanticipated problems involving risks to subjects or others.

These adverse events or unanticipated problems involving risks to subjects or others will be reported to the HIC or HSC within 48 hours of it becoming known to the investigator, using the appropriate forms found on the website.

**7) Plan for reporting adverse events to co-investigators on the study, as appropriate the protocol's research monitor(s), e.g., industrial sponsor, Yale Center for Clinical Investigation Research Subject Advocates (RSAs), Cancer Center's Quality Assurance, Compliance and Safety Committee (QUACS) Protocol Review Committee (PRC), DSMBs, study sponsors, funding and regulatory agencies, and regulatory and decision-making bodies**

For the current study, the following individuals, funding, and/or regulatory agencies will be notified (choose those that apply):

All Co-Investigators listed on the protocol.

Yale Center for Clinical Investigation Research Subject Advocates (RSAs)

Quality Assurance and Compliance and Safety Committee (QUACS)

National Institutes of Health

Food and Drug Administration (Physician-Sponsored IND #\_\_\_\_\_)

Medical Research Foundation (Grant\_\_\_\_\_)

The principal investigator, [name], will conduct a review of all adverse events upon completion of every study subject. The principal investigator will evaluate the frequency and severity of the adverse events and determine if modifications to the protocol or consent form are required.

